7.1.	Reporting Precision	32
8.	PROGRAMMING SPECIFICATIONS	33
9.	MOCK TABLES, LISTINGS AND GRAPHS (TLGS)	34
10.	REFERENCES	35
	APPENDIX I ALK8700-A302 PART A SAP	36
	APPENDIX II AESI SEARCH CRITERIA	37

ABBREVIATIONS

The following abbreviations are used in the statistical analysis plan.

Abbreviation or Term	Explanation or Definition
AE	Adverse Event
AESI	Adverse Events of Special Interest
ALK-P	Alkaline Phosphatase
ALT	Alanine Aminotransferase
ANCOVA	Analysis Of Covariance
AST	Aspartate Aminotransferase
ATC	Anatomical Therapeutic Chemical [Classification System]
BID	Bis In Die [Twice A Day]
BMI	Body Mass Index
BUN	Blood Urea Nitrogen
CI	Confidence Interval
C-SSRS	Columbia Suicide Severity Rating Scale
DMC	Data Monitoring Committee
DMF	Dimethyl fumarate (Tecfidera®)
DMT	Disease Modifying Treatment
ECG	Electrocardiogram
eCRF	Electronic Case Report Form
[REDACTED]	[REDACTED]
[REDACTED]	[REDACTED]
[REDACTED]	[REDACTED]
ET	Early Termination
FAS	Full Analysis Set
FS	Functional System
GdE	Gadolinium-Enhancing
GGISIS	Global Gastrointestinal Symptom And Impact Scale
GI	Gastrointestinal
HDL	High Density Lipoprotein
IGISIS	Individual Gastrointestinal Symptom And Impact Scale
LDH	Lactic Dehydrogenase

Abbreviation or Term	Explanation or Definition
LDL	Low Density Lipoprotein
LLN	Lower Limit Of Normal Range
MedDRA	Medical Dictionary For Regulatory Activities
MMF	Monomethyl Fumarate
MRI	Magnetic Resonance Imaging
MS	Multiple Sclerosis
NCI-CTCAE	National Cancer Institute Common Terminology Criteria For Adverse Events
PCS	Potentially Clinically Significant
PDEAE	Post-discontinuation Emergent Adverse Event
[REDACTED]	[REDACTED]
PT	Preferred Term
QOL	Quality Of Life
QTcB	QT Interval Corrected Using Bazett's Formula
QTcF	QT Interval Corrected Using Fridericia's Formula
RRMS	Relapsing-Remitting Multiple Sclerosis
SAE	Serious Adverse Event
SD	Standard Deviation
[REDACTED]	[REDACTED]
[REDACTED]	[REDACTED]
[REDACTED]	[REDACTED]
SOC	System Organ Class
[REDACTED]	[REDACTED]
TEAE	Treatment-Emergent Adverse Event
ULN	Upper Limit Of Normal Range
WBC	White Blood Cells
WHO	World Health Organization

1. INTRODUCTION

This statistical analysis plan (SAP) describes the statistical methods and data presentations to be used for analyzing and reporting efficacy and safety data for study ALK8700-A302. This study evaluating the GI tolerability of ALKS 8700 and DMF was composed of two parts, Parts A and B. Both Parts A and B were identical in study design and included a 5-week, double-blind treatment period with 2 blinded treatment arms (ALKS 8700 and DMF). Part A was exploratory. Part A evaluated the utility of 2 gastrointestinal (GI) symptom scales (Individual GI Symptom and Impact Scale [IGISIS] and Global GI Symptom and Impact Scale [GGISIS]) and endpoints derived from the scales in assessing GI tolerability in adult subjects with relapsing-remitting multiple sclerosis (RRMS) after administration of ALKS 8700 or dimethyl fumarate (DMF). Part A also evaluated the safety and tolerability of ALKS 8700 in adult subjects with RRMS.

A total of 120 subjects were randomized to treatment in Part A of the study. A separate SAP and Clinical Study Report (CSR) for Part A study were finalized, while Part B of the study was ongoing as planned.

The primary, secondary and exploratory endpoints for the study were revised based on exploratory analyses of the results from Part A. Major changes to the protocol included:

- Change in primary, secondary, and exploratory endpoints
- Change in the analysis of primary, secondary, and exploratory endpoints
- Change in the analysis of the safety data
- Increase in number of subjects in Part B and for the study

This document has been prepared based on Protocol ALK8700-A302 v2.0 (Amendment 1.0) (dated 15 Dec 2016) [1], v 2.1 (incorporates Polish-specific Amendment 1.1) (dated 23 Aug 2017) [2], Amendment 2.0 (incorporated Administrative Change Memo 1) (dated 20 Sep 2018) [3] and Germany-specific Amendment 2.2 (incorporated Administrative Change Memo 2) (dated 14 Dec 2018) [4].

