1.1. Study Objectives

The objectives of this study are to:

- Evaluate the utility of two gastrointestinal (GI) symptom scales (Individual GI Symptom and Intensity Scale [IGISIS] and Global GI Symptom and Intensity Scale [GGISIS]) and endpoints derived from the scales in assessing GI tolerability in adult subjects with relapsing remitting multiple sclerosis (RRMS) after administration of ALKS 8700 or dimethyl fumarate (DMF) in Part A
- Compare the GI tolerability of ALKS 8700 and DMF in adult subjects with RRMS using two GI symptom scales (IGISIS and GGISIS) with endpoints informed from Part A
- Evaluate the safety and tolerability of ALKS 8700 in adult subjects with RRMS in Parts A and B

Part A CSR presented the results of evaluation of utility of two GI Symptoms scales, IGIGIS and GGISIS and endpoints derived from these scales in assessing GI tolerability in adult subjects with relapsing remitting multiple sclerosis (RRMS) after administration of ALKS 8700 or dimethyl fumarate (DMF) in Part A.

In this study, GI tolerability of ALKS 8700 and DMF in adult subjects with RRMS will be compared with revised endpoints and safety and tolerability of ALKS 8700 will be evaluated based on pooled data from Part A and B.

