1.2. Summary of the Study Design

This is a randomized, double-blind, multicenter study to evaluate the tolerability of ALKS 8700 and DMF in adult subjects with RRMS. The study was conducted in two parts (Parts A and B). The study design is an adaptive approach where data from Part A was used to modify the GI tolerability endpoint(s) in the study.

Both Parts A and B are identical in study design and include a 5-week, double-blind treatment period with two blinded treatment arms (ALKS 8700 and DMF). Part A is exploratory. The first 120 eligible subjects will be randomized to one of the two treatment groups in Part A (n=60 per group). Once the randomization for Part A is complete, the next 380 eligible subjects will be randomized into one of the two treatment groups in Part B (n=190 per group). Accordingly, subjects 1-120 will be randomized into Part A and subjects 121-500 will be randomized into Part B. Subjects randomized in Part A will not be eligible to participate in Part B.

Following completion of Part A, the sponsor conducted a planned, unblinded analysis of the Part A GI tolerability and safety data. Part B will be ongoing during the analysis of the Part A data. Data from Part A can be used to modify the Part B GI tolerability endpoint(s). Pooled GI tolerability data from Part A and Part B will be analyzed for the primary and secondary endpoints.

All study visits in Parts A and B will be completed on an outpatient basis. The screening period is up to 4 weeks (28 days) including a 1-week lead-in period (prior to randomization) during which subjects will complete two self-administered GI symptom scales daily using e-diaries.

In Part A and Part B, subjects meeting the eligibility criteria will be randomized in a 1:1 ratio to one of two blinded treatment groups as follows:

- Group 1: ALKS 8700 462 mg BID (with 1-week titration)
- Group 2: DMF 240 mg BID (with 1-week titration)

In each part, both ALKS 8700 and DMF will be administered orally BID as blinded study drug; either ALKS 8700 462 mg BID or DMF 240 mg BID with an initial 1-week dose titration period. Subjects will be instructed to take study drug with or without food. However, subjects will be instructed to avoid taking study drug with a high-fat, high-calorie meal. Dosing is described in detail in Protocol Section 9.1.

[figure not shown]

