2. SAMPLE SIZE AND STATISTICAL POWER CONSIDERATION

Sample Size Considerations (Part A and Part B): The sample size calculation for Part B is based on the secondary endpoint of the mean number of days with any IGISIS individual symptom intensity score ≥ 2 .

Assuming the mean number of days with any IGISIS individual symptom intensity score ≥ 2 is 3.5 and 2.0 for the DMF and ALKS 8700 treatment groups, respectively, a sample size of 500, including 60 randomized subjects per group (120 subjects in total) in Part A and 190 randomized subjects per group (380 subjects in total) in Part B, will provide at least 80% power to detect about a 42% reduction in the number of days with any IGISIS individual symptom intensity score ≥ 2 for the ALKS 8700 treatment group relative to the DMF treatment group, at an alpha level of 0.05 (two-sided) using a negative binomial regression approach. The sample size calculation assumes a standard deviation of 5.9 in the number of days with any IGISIS individual symptom intensity score ≥ 2 relative to exposure days for the DMF treatment group in Part A and Part B.

Assuming the mean number of days with any IGISIS individual symptom intensity score ≥ 2 is 3.5 and 2.0 for the DMF and ALKS 8700 treatment groups, respectively, a sample size of 380 randomized subjects (190 subjects per treatment group) in Part B will provide at least 80% power to detect about a 42% reduction in the number of days with any IGISIS individual symptom intensity score ≥ 2 for the ALKS 8700 treatment group relative to the DMF treatment group, at an alpha level of 0.05 (two-sided) using a negative binomial regression approach. The sample size calculation assumes a standard deviation of 5.9 in the number of days with any IGISIS individual symptom intensity score ≥ 2 relative to exposure days for the DMF treatment group in Part B.

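### The primary superiority test pools Part A with Part B at an unadjusted 5% after endpoints, analysis and sample size were changed following an unblinded look at Part A, so the stated 5% is not assured

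*SAP*

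**What the plan says.** Sections 1 and 1.2 of the SAP call Part A exploratory. Section 1.2 reports that "the sponsor conducted a planned, unblinded analysis of the Part A GI tolerability and safety data" while Part B was running. On the consequence, Section 1 is direct: "The primary, secondary and exploratory endpoints for the study were revised based on exploratory analyses of the results from Part A". Its list of major protocol changes also includes the analysis of those endpoints and the number of subjects in Part B and overall. It does not give the earlier size or say what drove the increase.

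Section 1.2 then says: "Pooled GI tolerability data from Part A and Part B will be analyzed for the primary and secondary endpoints". Section 3.6.2 accordingly makes the primary endpoint the number of days with an IGISIS score of 2 or more in both parts together. The same endpoint in Part B alone is the first secondary endpoint. Section 3.6.1 sets a two-sided 5% level with no multiplicity correction. Section 3.6.2.1 allows a superiority claim when p is below 0.05 and the estimate favours that arm. The model adjusts for study part.

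Section 2 sizes both analyses. For the second it says that "a sample size of 380 randomized subjects (190 subjects per treatment group) in Part B will provide at least 80% power".

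**The concern.** Data that helped to choose a hypothesis are counted again as evidence for it. If the endpoint was kept because the Part A treatment difference looked good on it, that favourable chance deviation goes into the pooled statistic, which is then compared with an ordinary 1.96 limit. The study-part covariate does not repair this. It absorbs a difference in symptom level between the parts, while a selected treatment contrast within Part A stays in the pooled treatment effect.

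The sample-size increase opens a second route. If it responded to the Part A contrast, the weight of Part A in the pooled test depends on the Part A result, and the fixed-sample limit no longer guarantees 5%.

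At stake is the reading of a pooled p-value just under 0.05. As written, it permits a superiority claim even when Part B alone does not support one, and the pooled rate ratio may be shifted.

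**Working it through.** **1. The plan's own power figure.** Inputs from Section 2: means 3.5 (DMF) and 2.0 (ALKS 8700), SD 5.9 for DMF, two-sided 5%, negative binomial model, 250 or 190 per arm. Assumption: the same dispersion k in both arms, since the SAP gives an SD for DMF only.

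- k = (5.9² − 3.5)/3.5² = 2.556; log(3.5/2.0) = 0.560.
- SE(log RR) = sqrt((1/3.5 + 1/2.0 + 2k)/n).
- Pooled, n = 250: SE 0.154, power 95.4%.
- Part B, n = 190: SE 0.176, power 88.8%.

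Both agree with the stated minimum of 80%.

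**2. Weight of Part A.** 120/500 = 0.24, so approximately Z(pooled) = sqrt(0.24)·Z(A) + sqrt(0.76)·Z(B), rejecting when |Z| > 1.96.

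**3. Effect of endpoint selection, no true effect.** Assumptions, because the visible text gives none: K candidates in Part A with equal pairwise correlation, one kept by its Part A result. Rule (a) keeps the candidate most favourable to ALKS 8700. Rule (b) keeps the largest difference in either direction. Rule (a) was obtained by numerical integration and checked by simulation; rule (b) by simulation with 2,000,000 runs per setting.

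| K | Correlation | (a) False ALKS 8700 superiority (nominal 2.5%) | (a) Two-sided error | (b) Two-sided error |
|---|---|---|---|---|
| 3 | 0.5 | 4.35% | 5.37% | 7.43% |
| 3 | 0.8 | 3.65% | 5.15% | 6.63% |
| 3 | 0.9 | 3.30% | 5.08% | 6.16% |
| 6 | 0.5 | 5.75% | 6.39% | 9.41% |
| 6 | 0.8 | 4.40% | 5.56% | 7.76% |
| 6 | 0.9 | 3.79% | 5.28% | 6.91% |
| 10 | 0.5 | 6.87% | 7.33% | 10.98% |
| 10 | 0.8 | 4.96% | 5.94% | 8.61% |
| 10 | 0.9 | 4.14% | 5.47% | 7.42% |

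Under rule (a) the pooled rate ratio centres at 0.92 to 0.98 instead of 1 (mean 3.5 in both arms, n = 250, SE 0.151). With one candidate, the level is 5%.

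**4. Effect of the sample-size increase alone.** The earlier size is not given. Suppose the Part B size per arm, n(B), could have been set anywhere in a range after seeing Z(A). With w = 60/(60 + n(B)), take for each Z(A) the size that maximises 1 − Φ((1.96 − sqrt(w)·Z(A))/sqrt(1 − w)), and average over Z(A). The worst-case one-sided error is 3.1% for 60 to 190 per arm and 2.7% for 120 to 190, against 2.5% with the size fixed.

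**5. The alternatives.** Part B subjects are different people, so Z(B) is independent of any choice made from Part A. The Part B-only test keeps 2.5% per side and 5% two-sided in every setting above. If the pooled claim also requires Part B to be significant in the same direction, its two-sided error cannot exceed that 5%. Under rule (a) it is 2.7%, with false ALKS 8700 superiority of 1.6% to 2.2%.

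**6. Power of the alternatives.** Same inputs as step 1. For the gate, pooled and Part B statistics have correlation sqrt(0.76) = 0.872.

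| Assumed loss | Pooled | Part B alone | Pooled gated on Part B |
|---|---|---|---|
| 0% | 95.4% | 88.8% | 88.1% |
| 10% | 93.3% | 85.4% | 84.5% |
| 20% | 90.3% | 81.1% | 79.8% |

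**The case against.** The adaptation was planned and is disclosed, and the untouched analysis is already in the SAP: first-listed secondary, with its own model and its own power statement. A reader will see that result. This stands and limits the severity. It does not make the claim depend on that result.

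A reader might infer that no selection rule exists. The documents do not support that. Section 1 says "A separate SAP and Clinical Study Report (CSR) for Part A study were finalized", but only the heading of Appendix I, which should hold the Part A SAP, is available, and the protocol is not shown. The point therefore rests on the ordering of the two analyses in the SAP, not on a missing rule.

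A reader might also infer that the 5% level has been broken. That does not follow either. If no choice used the treatment contrast, the level holds, and at the mild end of rule (a) the two-sided error is only 5.1%. The opposite shortcut fails too: an endpoint rule blind to the contrast would not be enough, because the analysis and the sample size also changed.

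The claim rule in Section 3.6.2.1 does not name the data set. That it applies to the pooled data is an inference from Section 3.6.2, where the pooled endpoint is primary. The inference is reasonable.

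Finally, Section 4 says that no interim analysis was planned, and a reader might see a contradiction with Section 1.2. Since Part A had its own SAP and report, this can mean no interim look at Part B or the pooled data. It is a matter of terminology.

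**Conclusion.** The concern holds in this form: the SAP makes the pooled analysis primary at an unadjusted 5% after changes that followed an unblinded look at part of the same data, and it does not make the claim conditional on Part B. Following the plan as written can break the stated level.

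Whether it does, and by how much, cannot be determined from the documents. Neither selection scenario is an upper bound; both depend on assumed candidate counts, correlations and rules. The sample-size figure depends on an assumed range for the earlier Part B size. That Part B alone is protected assumes that the changes used Part A data and not unblinded Part B data. It should be fixed, because the remedy only re-orders two analyses that the SAP already contains.

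**What to change.** Decide and date the change before Part B is unblinded.

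- **Preferred.** In Section 3.6.2, let the Part B-only analysis of days with an IGISIS score of 2 or more carry the superiority claim. Report the pooled analysis as supportive, labelled as including the data used to revise the endpoint.
- **Smaller change.** Keep the pooled primary, but allow the claim only if Part B alone is also significant at two-sided 5% in the same direction. Report the Part B rate ratio beside the pooled one, because the gate does not remove bias from the pooled estimate.
- **When the pooled test may stand alone.** Only if a rule fixed before Part A was unblinded shows that the endpoint choice, the analysis model and the sample-size increase all made no use of the Part A treatment contrast. Section 3.6.2 should then cite it.
- **If Part B is already unblinded.** Leave the primary as planned, report the Part B result beside it and state the limitation.

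Cost: no new subjects, data or models. The SAP changes, and probably the protocol too, since Section 5 of the SAP reports no departures from it. Under equal dispersion, power for the claim falls by 6.6 points with Part B alone (95.4% to 88.8%) or 7.3 points with the gate (95.4% to 88.1%). At an assumed 20% loss, Part B alone still meets the stated 80%, while the gate falls just short of it.

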1.1. Study Objectives

The objectives of this study are to:

- Evaluate the utility of two gastrointestinal (GI) symptom scales (Individual GI Symptom and Intensity Scale [IGISIS] and Global GI Symptom and Intensity Scale [GGISIS]) and endpoints derived from the scales in assessing GI tolerability in adult subjects with relapsing remitting multiple sclerosis (RRMS) after administration of ALKS 8700 or dimethyl fumarate (DMF) in Part A
- Compare the GI tolerability of ALKS 8700 and DMF in adult subjects with RRMS using two GI symptom scales (IGISIS and GGISIS) with endpoints informed from Part A
- Evaluate the safety and tolerability of ALKS 8700 in adult subjects with RRMS in Parts A and B

Part A CSR presented the results of evaluation of utility of two GI Symptoms scales, IGIGIS and GGISIS and endpoints derived from these scales in assessing GI tolerability in adult subjects with relapsing remitting multiple sclerosis (RRMS) after administration of ALKS 8700 or dimethyl fumarate (DMF) in Part A.

In this study, GI tolerability of ALKS 8700 and DMF in adult subjects with RRMS will be compared with revised endpoints and safety and tolerability of ALKS 8700 will be evaluated based on pooled data from Part A and B.

1.2. Summary of the Study Design

This is a randomized, double-blind, multicenter study to evaluate the tolerability of ALKS 8700 and DMF in adult subjects with RRMS. The study was conducted in two parts (Parts A and B). The study design is an adaptive approach where data from Part A was used to modify the GI tolerability endpoint(s) in the study.

Both Parts A and B are identical in study design and include a 5-week, double-blind treatment period with two blinded treatment arms (ALKS 8700 and DMF). Part A is exploratory. The first 120 eligible subjects will be randomized to one of the two treatment groups in Part A (n=60 per group). Once the randomization for Part A is complete, the next 380 eligible subjects will be randomized into one of the two treatment groups in Part B (n=190 per group). Accordingly, subjects 1-120 will be randomized into Part A and subjects 121-500 will be randomized into Part B. Subjects randomized in Part A will not be eligible to participate in Part B.

Following completion of Part A, the sponsor conducted a planned, unblinded analysis of the Part A GI tolerability and safety data. Part B will be ongoing during the analysis of the Part A data. Data from Part A can be used to modify the Part B GI tolerability endpoint(s). Pooled GI tolerability data from Part A and Part B will be analyzed for the primary and secondary endpoints.

All study visits in Parts A and B will be completed on an outpatient basis. The screening period is up to 4 weeks (28 days) including a 1-week lead-in period (prior to randomization) during which subjects will complete two self-administered GI symptom scales daily using e-diaries.

In Part A and Part B, subjects meeting the eligibility criteria will be randomized in a 1:1 ratio to one of two blinded treatment groups as follows:

- Group 1: ALKS 8700 462 mg BID (with 1-week titration)
- Group 2: DMF 240 mg BID (with 1-week titration)

In each part, both ALKS 8700 and DMF will be administered orally BID as blinded study drug; either ALKS 8700 462 mg BID or DMF 240 mg BID with an initial 1-week dose titration period. Subjects will be instructed to take study drug with or without food. However, subjects will be instructed to avoid taking study drug with a high-fat, high-calorie meal. Dosing is described in detail in Protocol Section 9.1.

[figure not shown]
The study duration for each part is approximately 11 weeks, which includes up to 4 weeks for screening (including a 1-week lead-in period), a 5-week double-blind treatment period (with 1-week titration), and a 2-week follow-up period (for subjects not continuing into the ALK8700-A301 long-term safety study). During the 5-week treatment period (Visits 3-8),

subjects will return to the clinic for weekly scheduled visits for assessments of safety, tolerability, pharmacokinetics (in a subset of subjects in Part A at selected sites), and clinical status (see [Figure 1](#)). Any subject who prematurely discontinues from the study will return to the clinic for an ET visit (Visit 8) and a follow-up visit (Visit 9).

Subjects completing the entire 5 weeks of double-blind treatment in either Part A or Part B of the study will be eligible to enroll in a long-term, open-label safety study (Study [ALK8700-A301](#)) and receive ALKS 8700 for up to 96 weeks. Subjects not enrolling in the long-term safety study will return to the clinic 2 weeks following Visit 8 for a follow-up visit (Visit 9).

A schematic of the study design is provided in [Figure 1](#) below.

Figure 1: Study Design Schematic (Part A and Part B)

*Subjects completing the 5-week treatment period will either continue into the ALK8700-A301 long-term safety study or enter the safety follow-up period and return to Visit 9

[REDACTED]

Table 1: Schedule of Visits and Assessments

Visit	Screening		5-Week Randomized Treatment ¹							Follow-up
	1 ²	2 ³	3	4	5	6	7	8 (ET)		
Week	-4	-1 (±2 days)	1 (±3 days)	2 (±3 days)	3 (±3 days)	4 (±3 days)	5 (±3 days)	6 (±3 days)	7 (±3 days)	8 (±3 days)
Informed Consent	X									
Eligibility Criteria Review	X		X ⁴							
Demographics	X									
Medical History	X									
Height	X									
Weight	X		X ⁴						X	
Physical Exam ⁵	X		X ⁴						X	X
Concomitant Medication Review	X	X	X	X	X	X	X	X	X	X
Adverse Event Monitoring	X	X	X	X	X	X	X	X	X	X
Serology Testing ⁶	X									
Pregnancy Test ⁷	X		X ⁴							
Vital Signs ⁸	X		X ⁴	X	X	X	X	X	X	X
Standard 12-Lead ECG ⁹	X		X ⁴		X				X	X
Biochemistry, Urinalysis, & Hematology Samples ¹¹	X		X ⁴		X				X	X

Table 1: Schedule of Visits and Assessments (Continued)

	Screening		5-Week Randomized Treatment ¹							Follow-up 9
	1 ²	2 ³	3	4	5	6	7	8 (ET)		
Visit	1 ²	2 ³	3	4	5	6	7	8 (ET)	9	
Week	-4	-1 (±2 days)	1 (±3 days)	2 (±3 days)	3 (±3 days)	4 (±3 days)	5 (±3 days)	6 (±3 days)	7 (±3 days)	8 (±4 days)
Brain MRI	X ¹²									
IGISIS		X ¹³	X ¹⁴	X ¹⁴	X ¹⁴	X ¹⁴	X ¹⁴	X ¹⁴	X ¹⁴	
GGISIS		X ¹³	X ¹⁴	X ¹⁴	X ¹⁴	X ¹⁴	X ¹⁴	X ¹⁴	X ¹⁴	
C-SSRS ¹⁵	X		X ⁴		X				X	X
Randomization			X							
Study Drug Dispensation/Accountability			X	X	X	X	X	X	X	

Abbreviations: C-SSRS=Columbia Suicide Severity Rating Scale; ECG=electrocardiogram; [REDACTED]; ET=early termination; [REDACTED]; GI=gastrointestinal; GGISIS=Global GI Symptom and Impact Scale; IGISS=Individual GI Symptom and Impact Scale; MRI=magnetic resonance imaging; [REDACTED]

² To be conducted within 4 weeks (-28 days) of randomization (Visit 3).

³ To be conducted 1 week before Visit 3 (Week 1/Randomization). The screening period (Visit 1 to Visit 3) may last up to 28 days.

[figure not shown]
A complete physical examination at screening (Visit 1); a brief physical examination at all other scheduled visits.

⁶ Serology testing includes hepatitis B surface antigen, hepatitis C antibody, and human immunodeficiency virus antibody.

⁷ Serum pregnancy at screening (Visit 1); urine pregnancy at randomization (Visit 3).

⁸ Vital sign measurements include temperature, respiratory rate, blood pressure, and heart rate. Vital signs to be collected predose at randomization (Visit 3) and at any time at all other scheduled visits. Blood pressure, respiratory rate, and heart rate will be measured after the subject has been in a seated or supine position for at least 5 minutes.

⁹ ECGs to be collected predose at randomization (Visit 3) and at any time at all other scheduled visits. ECGs will be collected after the subject has been in a supine position for at least 5 minutes.

¹¹ Urinalysis includes urine dipstick, urine microscopy (as applicable), urine beta-2-microglobulin, urine albumin, and urine creatinine.

¹² MRI to be performed at any time between screening (Visit 1) and randomization (Visit 3) provided all other screening criteria have been checked for subject eligibility. MRI must not be performed within 30 days of receiving a course of steroids.

¹³ The IGISIS will be completed twice daily (with at least 6 hours in between each completion) and the GGISIS will be completed once daily using e-diaries during the 1-week lead-in period prior to randomization (Visit 3).

¹⁴ The IGISIS will be completed twice daily (should be completed within 9 hours after taking each dose of study drug) and the GGISIS will be completed once daily (each morning prior to taking the morning dose of study drug) using e-diaries during the randomized treatment period (Visit 3 to Visit 8).

¹⁵ Use "Screening" version at screening (Visit 1) and "Since-Last-Visit" version for all subsequent time points.

